# 6 Investigational Product

Investigational product (IP) utilized in this protocol is FCX-007 (genetically modified autologous human dermal fibroblasts suspended in DMEM).

One administration of FCX-007 is up to 15 mL of cell suspension administered as sixty (60) 0.25 mL intradermal injections. **Table 1** provides details regarding the number of cells, vials and injections per administration.

Table 1 - FCX-007 Cell Count and Injections per Administration

# 6.1 Manufacturing

### 6.1.1 FCX-007 Manufacturing

FCX-007 will be manufactured from one set of three 3-4 mm biopsies obtained at the Screening Visit. The biopsies will be placed into sterile phosphate buffered saline (PBS), and shipped at 2-8°C immediately to the manufacturing facility. Upon receipt of the biopsies, FCX-007 will be manufactured by gene modification and expansion of dermal fibroblasts obtained from the biopsy. The tissue will be digested with enzymes to release the fibroblasts, which will then be seeded into a tissue culture vessel. The cells will be expanded, transduced with INXN-2004 (a lentiviral vector encoding the functional COL7A1 gene), and expanded further. If the manufacturing process does not yield an FCX-007 cell count sufficient for at least one administration, or does not meet manufacturing release specifications, an additional set of biopsies may be requested from the subject.

For each subject, approximately will be manufactured for use in this study. Up to will be administered at each dose administration. Cells undergo release testing and sent to the Investigative Site for administration on Day 0. The duration between biopsy collection and completion of manufacturing is approximately 120 days (4 months) but can vary due to capacity, technical manufacturing reasons, or clinical protocol required pauses between subjects.

CONFIDENTIAL Page 23 of 75

Final Version 8.0, 29 Oct 2019

# 6.2 Labeling, Packaging, Storage and Handling

### 6.2.1 Packaging and Labeling

### 6.2.1.1 Packaging

Investigational product will be provided to the Investigative Site as an opaque cell suspension in 2.0 mL cryovials containing approximately 1.2 mL of FCX-007 per vial with a recoverable volume of 1.0 mL per vial.

Up to thirty (30) vials of FCX-007 will be provided per subject; 15 vials for Day 0, and 15 vials for week 4.

### 6.2.1.2 Labeling

The vials will be labeled with a minimum of the subject number and the date of manufacture. The secondary container in which the vials are shipped will include the following information:

- IP Name: FCX-007

- Lot Number
- Fill Date and Time
- Expiration Date and Time
- Nominal Conc./Vol.: xe7 cells/mL in 1.0 mL
- Manufactured by Fibrocell Technologies Inc.
- CAUTION: NEW DRUG Limited by US Federal Law to Investigational Use
- NOT EVALUATED FOR INFECTIOUS SUBSTANCES

The cells will be transported to the investigative site as a suspension and the vial will be packaged in a temperature controlled and monitored shipper and delivered by overnight courier.

### 6.2.2 Storage and Handling

After receipt of the shipped vials, they must be kept sealed in the shipper until ready for use. The Investigator will be responsible for accurate, written records of all FCX-007 received. The Sponsor or designee will be permitted upon request to audit the administration procedures and records.

FCX-007 Drug Product will be shipped same day or overnight delivery to the clinic and must be administered prior to the expiration date and time indicated on the product label.

CONFIDENTIAL Page 24 of 75

Final Version 8.0, 29 Oct 2019

# 7 Study Visits

This section outlines activities by visit. Additional information about specific procedures and evaluations can be found in Section 8 (Procedures: FCX-007 Administration to Intact Skin), Section 9 (Procedures: FCX-007 Administration to Wound(s)), and Section 10 (Procedures: Collection and Evaluation of Biopsies). Study tests and procedures will be performed only after a signed informed consent is obtained.

During the study, every effort should be made to adhere to the visit schedule and visit windows provided in the Schedule of Events (**Table 2**).

### **Subject Companions**

Subjects will be permitted to bring a companion to study visits. Cost associated with travel to the Investigative Site, including those of a companion, will be paid for by the sponsor with prior approval from the sponsor.

### **Time Frame Between Subjects**

The second subject in each arm will not be treated until after the first subject has completed the 4-week evaluation. The DSMB will meet after the first subject has completed visit 5 (Week 4) to review data and determine whether the second subject in each arm can be treated. Likewise, the fourth subject (and first potential pediatric subject) in each arm will not be treated until after the third subject has completed the 4-week evaluation and the DSMB has reviewed the data. DSMB and FDA approval will be required prior to enrollment of any pediatric subject.

CONFIDENTIAL Page 25 of 75

FI-EB-001

Fibrocell Technologies

RDEB Phase I/II Protocol

Final Version 8.0, 29 Oct 2019

Table 2 - Schedule of Events

				Trea	tment F	Period							
Event	Pre- screen	Visit 1 Screen¹	Wound Monitoring Period 	V2 Day -2 	V3 Day 0	V4 Day 2	V5 Wk 4 ± 2d	V6 Wk 12 ± 1wk	V7 Wk 16³	V8 Wk 25 ± 2wk	V9 Wk 32 	V10 Wk 52 ± 2wk	LTFU
Information Letter and Phone Screen	Х												
ICF/ Assent/ HIPAA		Х											
Inclusion / Exclusion Criteria	Х	Х		X	Х								
Demographics	Х	X											
Medical / Medication History	Х	X		X	Х			X					
Concomitant Medications					Χ	Х	Χ	X	Χ	X	Х	X	
Adverse Events					Х	Х	Χ	X	Χ	X	X	X	X
Physical Exam		X			Х							Х	
Skin Exam 		Х	X	Х	Х	Х	Χ	X	Χ	X	Х	X	
Vital Signs		Х		Х	Х	Х	Χ	X	Χ	X	Х	Х	
Digital Imaging of Wounds		Х	Х	Х	Х	Х	Х	Х	Χ	Х	Х	Х	
Target Wound Selection				Х									
Investigator Assessment of Wound Healing							X	Х	Х	Х	Х	Х	
Bacterial Culture 				X	Х	Х	Χ	Х	Х	Х	Х	Х	
FCX-007 Administration					Х		Х						
Urine Pregnancy Test		Х		X									
Hematology & Chemistry		Х		X			Χ	Х	Χ	Х	Х	Х	
HIV, Hep B, Hep C Testing		Х											
RCL evaluation			X 				Χ	Х	Х	Х	Х	Х	X12
C7 Antibody Assay		Х					Χ	Х	Χ	Х	Х	Х	
Genetic Testing		Х											

### Continues on next page

CONFIDENTIAL Page 26 of 75

<sup>1 Visit 1 protocol events may take up to 4 days. Screening assays for RDEB diagnosis will not be repeated unless warranted by the Investigator if the subject medical records contain these results.

<sup>2 At least two visits to the site for imaging during the approximate 4 month period in which FCX-007 is being manufactured may occur. The last wound monitoring visit should occur no more than 60 days prior to the injection of FCX-007.

<sup>3 Visits 7 and 9 can be performed in the office or via telephone consult. If visit is conducted via telephone consult, only concomitant medication and adverse event reporting from subject will be recorded.

<sup>4 Subjects can remain at or near the Investigative Site between Visits 2 and 4.

<sup>5 Skin exam on potential target wounds only during wound monitoring visits.

<sup>6 To be performed at Visit 2 and as needed throughout the study if clinical evaluation is indicative of infection.

<sup>7 A blood sample must be collected for RCL baseline assessment either at screening or wound monitoring visits, results must be available prior to Visit 3 (Day 0).

FI-EB-001

Fibrocell Technologies RDEB Phase I/II Protocol Final Version 8.0, 29 Oct 2019

Table 2 - Schedule of Events, Continued

Eve	ent		Pre- screen	Visit 1 Screen	Wound Monitoring Period	V2 Day -2	V3 Day 0	V4 Day 2	V5 Wk 4 ± 2d	V6 Wk 12 ± 1wk	V7 Wk 16	V8 Wk 25 ± 2wk	V9 Wk 32	V10 Wk 52 ± 2wk	LTFU
		3-4 mm for FCX-007 facture 		Х											
	_	1 for IEM		X 			X	_		X		X		Х	
	Skir	1 for IF and DIF		X 			X		X	X		X		X	
Biopsies 	Intact Skin	1 for genomic retention of C7 and mRNA expression 					X		X	X		X		X	
Ш	V11 (150)	1 for IEM								X		X		X	
	Wounds	1 for IF and DIF								X		X		X	
	Mo	1 for genomic retention of C7 and mRNA expression							Х	х		X		X	

<sup>8 The number of biopsies collected at a visit may vary based on results from previous visits.

CONFIDENTIAL Page 27 of 75

<sup>9 An additional set of biopsies may be collected if the manufacturing process does not yield an FCX-007 cell count sufficient for one administration or do not meet release specifications.

<sup>10 Evaluations do not need to be performed if the subject meets inclusion criteria for RDEB diagnosis.

<sup>11 Samples cannot be shipped on Fridays.

<sup>12 RCL evaluation yearly for up to 15 years. If all post-treatment assays are negative during the first year (e.g., Weeks 4, 12, 16, 25, 32, and 52), collection of the yearly follow-up samples will be discontinued.

Final Version 8.0, 29 Oct 2019

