### 7.3.1 Visit 2 (Wound Selection/Run-In)

Visit 2 procedures may occur up to 2 days (±1 day) prior to the day of FCX-007 administration. The following procedures will be performed during Visit 2:

- Re-evaluation of inclusion/exclusion criteria
- Review of medical and medication history
- Skin Exam
- Vital signs: blood pressure, heart rate, respiratory rate, temperature
- Collection of blood (approximately 12.5 mL) for laboratory tests
  - Serum chemistry
  - Hematology
- Collection of urine for pregnancy test, if applicable
- Bacterial culturing of target wounds
- Final target wound selections of up to 3 pairs from the selected potential target wounds (See Section **9.1** for details)
- Label the selected target wound pairs as T1A and T1B for the 1st pair, T2A and T2B for the 2nd pair, and T3A and T3B for the 3rd pair.
- Digital imaging of wounds.

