## 10 Procedures: Collection and Evaluation of Biopsies

#### 10.1 Collection

Biopsies are collected according to **Table 2 - Schedule of Events**. Biopsy handling and shipping instructions are provided in **Appendix B: Biopsy Collection Procedures**. Unscheduled biopsies or laboratory tests may be performed as necessary to evaluate inflammation, possible SCC growths, or suspected presence of C7/anchoring fibrils (wound healing).

At Visits 5 (Week 4), 6 (Week 12), 8 (Week 25) and 10 (Week 52), up to four (4) and a minimum of three (3) biopsies will be collected:

- Two (2) biopsies from intact skin
  - One for IF and DIF analysis to evaluate
    - C7 expression (IF)
    - C7 antibodies (DIF)
  - One to evaluate C7 mRNA and DNA
- One (1) from the target wound to evaluate C7 mRNA and DNA

At other Visits the Investigator may collect up to six (6) biopsies per visit.

The number and type of biopsies obtained will ultimately depend on the judgment of the Investigator and Sponsor.

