#### 10.1.1 Collection Location

At all follow-up visits, biopsies are to be collected as closely to the injection sites as possible. To aid in locating the injection sites, a transparent overlay of the injection sites can be generated from imaging which can be placed over the subject's wound / intact skin. Through use of the transparent overlay, aligned with the wound /intact skin according to the tattoos, biopsy sites are chosen that are in alignment with the injection sites. If more than one pair of wounds is included in the study, the target wound from which a biopsy is obtained may vary from visit to visit, at the discretion of the Investigator, to minimize subject discomfort.

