#### 14.6.2 Immunoelectron Microscopy / Production of Anchoring Fibrils

Biopsies collected for the purpose of IEM will be evaluated for the presence of anchoring fibrils, LH24 and mAb185 antibody staining and C7 expression. Evaluation of each item from each biopsy will be scored by a qualified reader. LH24 and mAb185 antibody staining and anchoring fibrils will be evaluated and considered to be present if a score of + is observed.

The percent of target wounds with a + score for each item evaluated will be reported at each post-treatment visit by treatment for each study phase. For quantitative analysis, the obtained results will be assigned a numeric value of 0 and 1, respectively, for – and +. Change in score from baseline will be evaluated and reported for each post-treatment visit by treatment and study phase and compared between treatments for each study phase. These analyses will be performed for both FAS and PP populations.

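### Biopsy number, type and wound may depend on earlier results or on investigator judgment, so the per-visit C7 and anchoring-fibril rates may come from an outcome-selected sample

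*Combined protocol and SAP*

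**What the plan says.** Secondary objective 1 (Section 2.2.2) evaluates C7 expression and anchoring fibrils in biopsies at Weeks 4, 12, 25 and 52 and at unscheduled visits. Four provisions decide which tissue is examined:

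- **Table 2, footnote 8**, attached to the whole biopsy block: "The number of biopsies collected at a visit may vary based on results from previous visits". No rule says which results count or in which direction.
- **Section 10.1**: "The number and type of biopsies obtained will ultimately depend on the judgment of the Investigator and Sponsor". For Visits 5, 6, 8 and 10 it also gives a range, "up to four (4) and a minimum of three (3) biopsies will be collected", and lists three: intact skin for IF/DIF, intact skin for C7 mRNA and DNA, and target wound for C7 mRNA and DNA.
- **Section 10.1, unscheduled biopsies**: permitted for inflammation, possible carcinoma, or where healing suggests that C7 or fibrils are present.
- **Section 10.1.1**, where a subject has more than one pair: "the target wound from which a biopsy is obtained may vary from visit to visit, at the discretion of the Investigator, to minimize subject discomfort". Section 7.3.1 allows up to three pairs.

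On the analysis side, Section 14.6.1 reports change in IF score per visit by treatment. For IEM, Section 14.6.2 states: "The percent of target wounds with a + score for each item evaluated will be reported at each post-treatment visit". Section 14 counts unscheduled visits as treatment visits. Section 14.9 plans no imputation for efficacy analyses, though other assumptions may be explored. No section says which wounds form the denominator when some are not biopsied, or how unscheduled biopsies enter the rates.

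**The concern.** A percent positive at Week 12, 25 or 52 estimates the rate among treated wounds only if the reason a wound was biopsied is unrelated to its likely result. The plan does not secure this. If biopsies continue mainly after a positive, later positivity and persistence are overstated. If they stop once a positive is found, later positivity is understated. If the wound is chosen partly by how it looks, each visit's rate moves with that choice, and a change from baseline may compare different wounds.

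The person choosing appears to know the assignment. Section 9.2 has the investigator assign the wounds, the control is untreated, and no masking is described. That is an inference from these facts, not a statement in the protocol.

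The stake is mainly the reading of secondary objective 1. There is a second use: under Section 11.1.2.1, a C7 increase or mature fibrils in a single treated wound counts as evidence of benefit when the DSMB considers pediatric enrolment on data through Week 4. Table 2 marks no wound IF or IEM biopsy at Week 4, so either tissue criterion in a wound would then rest on discretionary or unscheduled sampling. The third criterion, investigator-assessed healing, needs no biopsy.

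**Working it through.** The documents give no rate, effect size or power for these endpoints, so there is no figure to reproduce. The first step uses the documents' own counts. The others are illustrations on assumed values.

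**1. How much of the biopsy set is discretionary.** Table 2 marks 3 biopsies at Visit 5. At each of Visits 6, 8 and 10 it marks 6: IEM, IF/DIF and mRNA/DNA, from intact skin and from wounds. Section 10.1 allows 3 to 4 at these visits and names three of the six. That leaves 6 − 3 = 3 others (intact-skin IEM, wound IEM, wound IF/DIF) for at most 4 − 3 = 1 place. Under the Section 10.1 ceiling, at least two of the three are omitted at each of these visits, and no text says which. Wound C7 by IF and all fibril data come from this part. Section 10.2.2 adds a further difference: it lists IEM at Visits 3, 8 and 10, without the Week 12 IEM that Table 2 marks.

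**2. Choice of wound.** Assume a true positive rate p = 0.30 in each of k independent treated wounds.

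- Limit, if a positive wound is always picked when there is one: 1 − (1 − p)^k. For k = 2, 1 − 0.7² = 0.51. For k = 3, 1 − 0.7³ = 0.66.
- Opposite limit, if a positive wound is always avoided when possible: p^k = 0.09 for k = 2 and 0.027 for k = 3.
- Partial guidance: each wound has a standard normal appearance score h and a fibril score c·h + √(1 − c²)·e, with e an independent standard normal. The wound is positive above the 70th percentile, and the best-looking wound is sampled (400,000 simulated subjects).

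| Correlation c | k = 1 | k = 2 | k = 3 |
|---|---|---|---|
| 0 | 0.30 | 0.30 | 0.30 |
| 0.3 | 0.30 | 0.36 | 0.39 |
| 0.6 | 0.30 | 0.42 | 0.49 |

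With one pair, or with a choice unrelated to outcome, there is no bias from this source.

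**3. Result-dependent repeat biopsy.** Assume the true rate stays at p = 0.30 and results at two visits have correlation ρ. If biopsies are repeated only after a positive, the later rate is p + ρ(1 − p). If only after a negative, it is p(1 − ρ).

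| ρ | Only after + | Only after − |
|---|---|---|
| 0.3 | 0.30 + 0.3 × 0.70 = 0.51 | 0.30 × 0.7 = 0.21 |
| 0.5 | 0.65 | 0.15 |
| 0.7 | 0.79 | 0.09 |

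A constant rate can thus look like a rise or a fall over time.

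**4. What omitted biopsies cost.** With no assumption about unsampled units, the interval between worst and best case has width (missing)/n. For n = 6, the planned maximum per phase, counting one wound per subject, 1, 2 or 3 missing give widths of 0.17, 0.33 or 0.50. For n = 12 they are 0.08, 0.17 or 0.25.

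**The case against.** The strongest reply is that these provisions protect subjects with fragile skin, some possibly as young as seven, and that none describes selection by outcome. The stated reason for changing wounds is discomfort, and there is no choice with one pair. Section 10.1 sets a minimum of three biopsies. Section 10.1.2 requires location and purpose to be recorded, so sampling is traceable. A qualified reader scores the tissue. The endpoints are secondary, the tests exploratory, and the study an unpowered pilot of about 12 subjects.

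Much of this stands. A reader might infer that the rates will come from a selected sample, or that the best-looking wound will be picked. The documents do not support either: they permit such sampling and do not show that it will occur. Nor do they say that the same wounds are followed throughout, since Section 14.6.2 is a per-visit summary. It would also be wrong to treat all C7 results alike. Intact-skin IF is in the listed minimum and is untouched by the choice among wounds, so it is less exposed, though the judgment clause in Section 10.1 covers it too.

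What does not answer the point: recording where a biopsy was taken does not make the sample representative, and a qualified reader does not control which tissue arrives. A choice made for comfort is unrelated to outcome only if comfort is unrelated to healing. Footnote 8 refers to results, not tolerance.

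**Conclusion.** The concern holds as a permitted and uncorrected risk, not as a demonstrated bias. Footnote 8 and Sections 10.1 and 10.1.1 let number, type and, with more than one pair, wound depend on earlier results or on the judgment of an investigator who appears to know the assignment. Section 14 does nothing to separate or adjust for this. Wound IF and all IEM data carry most of the risk. If the Section 10.1 ceiling is followed, some discretionary selection among them is unavoidable at Visits 6, 8 and 10.

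The direction is open and the size unknown. The illustrative 39% to 49% against a true 30%, with a limit of 66%, assumes three independent wounds and a choice guided by appearance. The bias is zero if choice is unrelated to outcome. No confirmatory error rate is affected. What suffers is the reading of C7 and fibril rates, especially their course over time. This is an inexpensive improvement worth making.

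**What to change.** 1. **Define the scheduled set.** Reconcile Table 2 (six biopsies at Visits 6, 8 and 10) with the Section 10.1 range of three to four, and with Section 10.2.2 (no Week 12 IEM). Which set is kept is not a statistical decision. It needs only to be stated in advance, and no biopsies need be added.
2. **Bar result-driven changes within that set.** Amend footnote 8 and Section 10.1 so that earlier IF, IEM or mRNA/DNA results do not decide which scheduled biopsies are taken. Keep omission for tolerance, safety or refusal, and record the reason.
3. **Name the pair at Visit 2.** In Section 10.1.1, set by fixed or random order the pair to be sampled at each visit. Using the same pair throughout, where tolerable, supports change over time. A rotation spreads discomfort and removes discretion but still compares different wounds, so report it as per-visit rates, not within-wound change.
4. **Separate triggered biopsies.** In Sections 14.6.1 and 14.6.2, exclude unscheduled biopsies prompted by healing or earlier results from the per-visit rates, and list them separately.
5. **State the denominator.** Report biopsied/eligible counts by visit and treatment, with best/worst-case bounds.

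The cost is wording in one footnote and a few sections, plus a recorded reason for each omission or switch. The downside is less freedom to choose the wound on the day.

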# 7.1 Screening Period

### 7.1.1 Prescreening

An Investigator or designee will prescreen medical histories of RDEB patients for potential inclusion into this study. Medical information reviewed may include the following and is dependent upon the Investigative Site's receipt of prior authorizations to access the data:

- NC1 status
- NC2 status as determined through LH24 antibody staining
- COL7A1 genotype of the subject
- C7 antibody history
- RDEB diagnosis results as determined by IF and EM/IEM
- Medical history
- Negative direct immunofluorescence (DIF)

The Investigator may request additional PHI disclosure authorizations from the potential subject to assist with Pre-Screening.

Potentially eligible subjects over the age of 18 are mailed an IRB-approved information letter which includes a study overview, key inclusion/exclusion criteria, information about the recruitment process, and contact information. For the Phase II portion of the study, parents of potentially eligible minors will be mailed the IRB-approved information letter.

If a potential subject or parent or guardian contacts the Investigative Site indicating interest in the study, they will be contacted by phone. An Investigator or designee reviews the letter with the subject or parent or guardian, and addresses questions. At this time the Investigator or designee can verbally review the inclusion / exclusion criteria. If the potential subject remains interested in participating in the study, a copy of the informed consent is sent to the potential subject to review.

### 7.1.2 Informed Consent

The Investigator will be responsible for obtaining from every subject prior to his/her participation in the study an ICF signed by the subject or legally authorized representative, in accordance with the Code of Federal Regulations, Title 21, Part 50.20. For subjects between the ages of 7 and 17 (inclusive), the Investigator is responsible for obtaining assent from the subject and consent from both parents or legal guardians. The ICF/Assent that is used must be the current version and must be approved by both the reviewing IRB and by the Sponsor. Informed consent/assent will be obtained from the subject after a full explanation of the purpose of the study, risks and discomforts involved, potential benefits, etc. have been provided by the Investigator both verbally and in writing. The original signed copy of the informed consent/assent must be maintained in the institution's records and is subject to inspection by a Sponsor representative.

CONFIDENTIAL Page 28 of 75

RDEB Phase I/II Protocol

Final Version 8.0, 29 Oct 2019

